
changes (constant controls and therapies, sudden change in the style of life, drug therapies and its effects, physical modifications), and that this can favor a mental reorganization of negative events, a greater expression and regulation of the emotions related to them, and the improvement of the relational style with family members and medical staff. Furthermore, this could be associated with a greater ability to cope with the consequences and psychophysical changes following transplantation and encourage greater levels of adherence with effects on the risk of organ rejection and health costs.

The hypothesis of the present study was that the expressive writing treatment produces an improvement in the emotional condition, levels of adherence and renal function, and a decrease in healthcare spending.

Material and Method

Thirty-five patients were recruited at the kidney transplant center of the Policlinico Umberto I, Sapienza University of Rome. Each participant completed an informed consent form. The sample was divided into two groups in a randomized way. Of the 35 patients, 3 were excluded for not completing the task, due to logistical problems and due to the hospital situation, 1 refused to perform the writing task, and finally 3 dropped to T2 (3rd post-transplant month). Of the remaining 28 recruited patients, 2 had an acute rejection before starting the writing task. The final sample is $n = 26$.

Each participant completed an informed consent form. Adult patients of Italian nationality with a sufficient level of education in order to understand the questionnaires and to execute the writing task were included in the study. Patients with uncompensated psychopathology, already excluded in the pre-transplant psychiatric evaluation, and / or affected by cognitive impairment, were excluded.

The study had 3 phases:

Pre-operative phase (T0)

The time of admission, just before the kidney transplant. In this phase to all participants were asked socio-demographic information and specific characteristics of the pathology in progress (eg. duration of dialysis treatment, date of transplantation, onset of disease). Then, they completed the following self-administered questionnaires: Beck Depression Inventory (BDI) for the evaluation of depression (Beck et al., 1961), State Trait Anxiety Inventory I and II (STAI Y1 - STAI Y2) for the evaluation of trait and state anxiety (Spielberger

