et al. , 1983), Toronto Alexythymia Scale 20-item (TAS-20) (Bagby et al., 1994) for assessing the ability to identify and describe one's emotions, Interpersonal Reactivity index (IRI) (Davis et al, 1980) for the evaluation of empathy and the Health Locus of Control (HLC) for the evaluation of the patient's beliefs on his state of health and a questionnaire for the evaluation of healthcare costs, built ad hoc. To assess the level of adherence, each patient answered to the following question: "Have you ever forgotten to take the drugs prescribed by your treatment plan?" with dichotomous answer yes / no. Finally, in order to assess the pre-transplant renal function values, such as Creatinine, CDK-EPI and azotemia, were collected.

Writing Phase (WP)

Five days after the operation, patients belonging to the experimental group, performed the writing task related to their deepest emotions, thoughts and concerns focused on the disease and the transplant itself, for 3 consecutive days, for 20 minutes a day. They did the writing session in a closed, silent room, which guaranteed their privacy. The instructions were according to the standard delivery by Pennebaker, creator of the technique (Pennebaker et al., 1986), translated and adapted for the specific hospital situation already proposed in a study on urological patients by Solano et al, 2007. Instead, the control group performed the neutral writing task, related to the description of an object in their room, without mentioning emotions, but just describing in a neutral way what they saw, for 3 consecutive days, 20 minutes each day.

The *day of discharge Phase (T1)* and *three months follow up (T2)* all participants filled the questionnaire completed before the operation and they had the blood analysis according to the hospital protocol for transplanted patients.

Statistical analysis

Statistical analysis will carry out using the software Statistica Soft 10.0. In order to evaluate the effectiveness of the expressive writing intervention, an analysis of variance with repeated measures (Fisher's F) and planned comparisons between the two randomized groups will be performed on psychological variables, the renal function indices and the health expenditure. The times taken into consideration will be T0, T1, T2 and the differences between T0, T1 and T2 will be respectively evaluated. To test the hypotheses on the dichotomous variable of adherence, Chi Square test will carry out.

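### The adherence test makes no stated use of the T0 answer, so with 26 patients a chance imbalance in prior forgetting can sway it

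*Combined protocol and SAP*

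**What the plan says.** The description of the pre-operative phase (T0) introduces the adherence measure: "To assess the level of adherence, each patient answered to the following question". The item is "Have you ever forgotten to take the drugs prescribed by your treatment plan", answered yes or no. For discharge (T1) and three months (T2) the protocol says that "all participants filled the questionnaire completed before the operation". This probably includes the adherence item, although the text does not name it.

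In the Statistical analysis section, repeated-measures analysis of variance with planned comparisons "will be performed on psychological variables, the renal function indices and the health expenditure". Adherence is not in that list. The section goes on: "The times taken into consideration will be T0, T1, T2 and the differences between T0, T1 and T2 will be respectively evaluated". Adherence then gets one sentence: "To test the hypotheses on the dichotomous variable of adherence, Chi Square test will carry out". It states no time point, stratification, covariate or paired method. Adherence is one of the four stated hypotheses, and this is its only named test.

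**The concern.** A patient who reported missed drugs before the transplant may well report them again afterwards, so the T0 answer is the natural prognostic factor for the T2 answer. An ordinary chi-square on arm by answer cannot use it.

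With about 13 patients per arm, randomisation will often leave one arm with several more prior forgetters than the other. If T0 predicts T2, that difference passes straight into the T2 table. A result in favour of expressive writing could then reflect who was forgetful beforehand. The T0 data needed to guard against this are already collected.

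**Working it through.** **Inputs from the documents.** Final sample 26; chi-square test for adherence; one yes/no item asked at T0.

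**Assumptions, because the documents give no figures.** 13 per arm; two-sided 5%; T0 'yes' rate 30-50%; T2 'yes' 80-90% after a T0 'yes' and 30-50% after a T0 'no' (control rates); for power, a common odds ratio of 1/4 or 1/8.

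**1. The plan's own figure.** Material and Method: 35 − 3 − 1 − 3 = 28, and 28 − 2 = 26. This agrees. There is no power, alpha or adherence rate to reproduce.

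**2. How often the arms are unbalanced at T0.** Take the T0 'yes' counts as two independent Binomial(13, p) variables.

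| p | P(difference ≥ 3, either direction) |
|---|---|
| 0.30 | 28.3% |
| 0.40 | 31.7% |
| 0.50 | 32.7% |

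By symmetry, the writing arm has 3 or more fewer in half of these, about 14-16% of randomisations.

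**3. What a difference of 3 does.** Shift = (3/13) × (T2 'yes' rate after T0 'yes' − rate after T0 'no').
- Smallest gap: 3/13 × (0.80 − 0.50) = 0.069, about 7 points.
- Largest gap: 3/13 × (0.90 − 0.30) = 0.138, about 14 points.

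Example for the largest gap, with 4 T0 'yes' patients in the writing arm and 7 in control, and no treatment effect. Expected T2 'yes' in the writing arm is 4 × 0.9 + 9 × 0.3 = 6.3 of 13 (48%). In control it is 7 × 0.9 + 6 × 0.3 = 8.1 of 13 (62%).

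**4. False rejection with no treatment effect (simulation).** The uncorrected Pearson chi-square on the T2 table is compared with the exact conditional test stratified by T0. The latter fixes the margins within each T0 stratum and sums the writing-arm 'yes' counts. Its mid-P value is P(less probable totals) + ½ P(equally probable totals).

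| | Chi-square | T0-stratified mid-P |
|---|---|---|
| All randomisations | about 6-8% | about 4-4.5% |
| Writing arm has ≥ 3 fewer T0 'yes' | about 7-16% | about 3-6% |

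The 7% at the low end is no worse than the chi-square's overall error rate. Imbalance therefore adds little where T0 predicts T2 weakly, and it matters where the link is stronger.

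**5. Dependence on the T0-T2 association.** With q the T0 'yes' rate, a and b the T2 'yes' rates after T0 'yes' and 'no', and m = qa + (1 − q)b, phi = (a − b) × √[q(1 − q) / (m(1 − m))].
- Weakest case: q = 0.3, a = 0.8, b = 0.5, m = 0.59, phi = 0.3 × √(0.21/0.2419) = 0.28.
- Strongest case: q = 0.5, a = 0.9, b = 0.3, m = 0.60, phi = 0.6 × √(0.25/0.24) = 0.61.

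Exact enumeration over a wider range of phi, for 4 or more fewer T0 'yes' patients in the writing arm and no treatment effect, gives chi-square rejection of 12-14% at phi 0.4, 21% at phi 0.6 and 32% at phi 0.8, nearly always in favour of writing. A Cochran-Mantel-Haenszel (CMH) test stratified by T0 rejects 3-5%. A difference of 4 or more in either direction occurs in 13-17% of randomisations.

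**6. Power.** At odds ratios 1/4 and 1/8 the uncorrected chi-square rejects as often as or more often than the stratified mid-P test in 13 of 16 settings, but its size is about 6-8%. Like for like, stratifying gains about 1-7 points (exact against exact) and 5-17 points (mid-P against mid-P). With size matched to at most 5%, enumeration of chi-square against stratified CMH gives about 0 at phi 0, +2 to +4 points at phi 0.4 and +8 to +11 at phi 0.6. The main limit is the sample: unadjusted power with 13 per arm is 25% for 50% v 25% and 42% for 40% v 10%, and 80% power would need 58 and 32 per arm.

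**The case against.** **The plan may not ignore T0.** The sentence on T0, T1, T2 and their differences comes just before the chi-square sentence and could be meant to cover adherence. A reader might infer that the plan has decided to discard T0; the documents do not say so. What stands is that no use of T0 is specified and no method for a binary change is named. The repair is the same either way.

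**Power.** A reader might infer that stratifying would raise power over the planned test. It does not: the uncorrected chi-square usually rejects as often or more often. Part of that comes from its excess size, which concerns the accuracy of the approximation and is a separate matter. The same excess explains part of the gap between the two tests in step 4. This objection stands, and the point does not rest on power.

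**The association is unknown.** The T0 answer concerns pre-transplant drugs and the T2 answer a new regimen, so a strong link cannot be assumed. This also stands. If T0 carries no information, imbalance does no harm and the size-matched gain is about zero.

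**Chance imbalance is not bias.** This is correct. Over all randomisations the chi-square's size in these settings is about 6-8%. The damage occurs in the particular trials that come out unbalanced, but a trial of 26 has a sizeable chance of being one of them.

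**Conclusion.** The point holds in conditional form. The T0 answer is collected, the other outcomes are analysed across all three times, and adherence alone has no specified use of baseline. If T0 predicts T2 as assumed, roughly one randomisation in three leaves a T0 difference of 3 or more patients, worth 7-14 percentage points or more in the T2 comparison. When that difference favours the writing arm, the chi-square's false rejection rate is about 7-16%, against about 3-6% with stratification.

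This is neither a systematic bias nor a power argument against the nominal chi-square. Low power comes mainly from n = 26, which stratification does not cure.

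All rates, the association and the 13:13 split are assumptions. At 16:10 the power comparison looks similar (about −1 to +2 points, size-matched, at phi about 0.4).

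The wording of the item adds to the case for using T0. Read literally, 'ever' means that a T0 'yes' cannot become a 'no', so those patients carry no information about the intervention. Stratification handles this in the analysis, but it does not repair the measure.

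**What to change.** Replace the chi-square sentence by:

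> The arms are compared on the T2 adherence answer with an exact conditional test stratified by the T0 answer (exact Cochran-Mantel-Haenszel, mid-P), with the common odds ratio and its exact 95% CI; the T1 comparison uses the same method and is secondary, and the unstratified 2x2 tables are descriptive.

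State that the adherence item is repeated at T1 and T2, and have it ask there about the period since transplant. The protocol describes recruitment and follow-up in the past tense. If the answers are already collected, the wording cannot be changed: state that as a limitation, and fix the analysis sentence before adherence is compared by arm.

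Cost: one sentence, a few more lines of analysis code and no new data. The nominal rejection rate will be somewhat below that of the oversized chi-square.
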